Effect of simplified insulin regimen on glycemic control and quality of life in an elderly population with type 2 diabetes

06/14/2023
NCT03660553

1) Protocol Title

Effect of simplified insulin regimen on glycemic control and quality of life in an elderly population with type 2 diabetes

2) IRB Review History*

Not applicable, the protocol has not been submitted for review by an external IRB.

3) Objectives*

Primary objective of this study is to test the hypothesis that once daily basal insulin (BI) is non-inferior to multiple subcutaneous injections (MSI) of insulin for glycemic control (HbA1c) in elderly patients with T2DM. A secondary aim of this study is to test that BI is superior to MSI for lowering HbA1c and is associated with lower incidence of hypoglycemia.

4) Background*

The prevalence of type 2 diabetes mellitus (T2DM) has been increasing over time, especially in the older age groups. According to the latest CDC data, 25.2% of the US population >65 years old has diabetes and it is expected to grow due to increase in life span as well as increase in incidence of T2DM [1, 2]. Many patients in this age group have other co-morbidities like heart disease, renal insufficiency, cognitive impairment, and lack of social support among others [3]. Elderly patients with T2DM are at an increased risk of hypoglycemia. Moreover, the benefits of tight glycemic control have not been established in this age group. Taking these factors into consideration, many professional organizations (American Diabetes Association, American Geriatrics Society) recommend relaxed glycemic goals (HbA1c ~8%) in the elderly population [4]. However, even for these relatively relaxed glycemic goals, insulin treatment is often necessary because due to associated comorbidities, many patients in this age group are poor candidates for non-insulin antidiabetic agents

[5]. Moreover, elderly patients with long standing T2DM may have decreased beta cell function and respond poorly to non-insulin antidiabetic agents [5].

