Currently, basal-bolus insulin therapy that includes one injection of long acting insulin and three injections of meal-time short acting insulin is the most commonly used insulin regimen. However, many older patients find the basal-bolus insulin regimen hard to manage due to the need of multiple injections and frequent blood glucose testing, especially in the setting of impaired vision, poor physical function and cognitive impairment [7]. If unsupervised, there are more errors with this regimen that can lead to hypoglycemia and hospitalization. Moreover, basal-bolus insulin regimen is stressful and expensive for the elderly patients, as well as time consuming for their care-givers. Many experts have tried a simplified regimen of basal insulin alone in the elderly patients (unpublished). In our experience, this simplified regimen is associated with less errors, improved glycemic control and dramatic improvement in the quality of life for the patient as well as their care-givers, without compromising glycemic control. However, there are no systematic studies comparing simplified insulin regimen versus the basal-bolus insulin regimen. We propose a study comparing single injection of basal insulin versus the usual basal-bolus insulin regimen in elderly patients (age >65 years) with T2DM. We believe this study will help in improving clinical care of elderly patients with T2DM and save healthcare costs.

5) Inclusion and Exclusion Criteria*

Inclusion Criteria

- Age >65 years
- Patient treated with an insulin regimen

Exclusion Criteria

- Unable to provide informed consent
- Enrollment in another research study
- History of hypoglycemia unawareness
- Pregnant women
- Prisoners

6) Number of Subjects*

We plan to recruit a total of 44 subjects from the outpatient clinic of the University of Miami including Diabetes Research institute and the Lennar Foundation Medical Center. We also recruit patients from the clinics at the Jackson Health System.

7) Study-Wide Recruitment Methods*

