Baseline characteristics will be summarized and compared to assure that the randomization algorithm resulted in comparable groups. Distributions will be evaluated and transformations to approximate normality will be considered if skewed. The main analysis will be an independent sample t-test or an analysis of covariance to allow for the inclusion of possible covariates such as age, baseline A1C, duration of diabetes, oral anti-diabetic medication use at baseline and number of comorbidities. 95% two-sided confidence interval (calculated on the basis of t-test or analysis of covariance) for the difference between BI and MSI treatment will be used for interpreting the results with regard to the non-inferiority margin. The main outcome variable will be the HbA1c after 6 months of treatment. Secondary outcomes will include mean glucose levels, hypoglycemic events, quality of life measures, patient satisfaction, and treatment failure.

The power calculation is based on the assumption that BI regimen will be non-inferior to MSI regimen for glycemic control. We anticipate that mean HbA1c in the control group (MSI group) at the end of treatment period will be 8.0% with standard deviation of 0.9. The study is designed to demonstrate a non-inferiority margin of 0.5, which is well within the margin of clinical relevance for this population. Group sample sizes of 18 in each group will achieve 95% power to detect non-inferiority using a two-sided, two-sample t-test with alpha 5%. Assuming a 20% drop-out rate, we plan to enroll 44 subjects into this study.

12) Provisions to Monitor the Data to Ensure the Safety of Subjects*

Follow-up and Laboratory test

Patients will be required to send their BG data to the study team every 3 days while the insulin doses are being adjusted and then every 1-2 weeks. Communication will be arranged via secure patient portal emails, telephone or clinic visits. HbA1C will be obtained at randomization and every 3 months after enrollment into the study.

13) Withdrawal of Subjects*

Subject withdrawal criteria

- Patient with severe hypoglycemia needing assistance or BG below 54 ng/dl after two insulin dose adjustments.
- Patient who develops hyperosmolar hyperglycemic syndrome.
- Patient with uncontrolled hyperglycemia >400 despite two insulin dose adjustments.
- Pregnancy during the study

14) Risks to Subjects*

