A relatively large dose of insulin glargine given in the morning may increase the risk of hypoglycemia. We will monitor patients closely and decrease the insulin dose as needed to prevent hypoglycemia. Any severe hypoglycemia in the BI group after two dose adjustments will lead to withdrawal from the study and conversion of insulin regimen to MSI.

There is also a risk of less tight glycemic control in the BI group as compared to the MSI group. However, a relatively high HbA1c is unlikely to cause any harm within the study period. Patients unable to achieve a lower HbA1c as compared to the baseline within first 3 months of the study will be withdrawn from the BI group and placed on MSI regimen.

15) Potential Benefits to Subjects*

Glucose control is likely to improve in all patients participating in this study. The main research intervention in this study will be decreasing the number of insulin injection to once daily instead of multiple daily injections. The remaining outpatient care for diabetes will be as per the ADA guidelines. Knowledge gained from this study may help simplify treatment of diabetes for the elderly patients with T2DM

16) Vulnerable Populations*

Children, incarcerated people and individuals with impaired decision-making capacity will be excluded from participating in the study. The study includes only the patients aged >65 years. Therefore, women of childbearing potential are excluded from this study. In spite of this, if a woman becomes pregnant, she will be immediately excluded from the study. However, we will follow them during the pregnancy for any potential complications that may be related to the study. Students and employees of the University of Miami are eligible for the study. Before they agree to participate, the students will be explained that their decision not to participate or to withdraw from the study will not affect their grades. Employees of the University of Miami will be explained that their decision not to participate or to withdraw from the study will not affect their employment at the University of Miami

17) Sharing of Results with Subjects*

The results of the study will be published in a peer review journal. If the results show that the BI group has significantly better outcomes, patients in the MSI group will be informed and given the option of change in their insulin regimen.

18) Setting

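### The stated 95% power with 18 per group does not follow from the stated inputs: at a true difference of zero it is about 37%.

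*Combined protocol and SAP*

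**What the plan says.** All the design inputs are in section 11, under Statistical Analysis.

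- **Control group:** mean HbA1c on MSI at the end of treatment "will be 8.0% with standard deviation of 0.9". No BI mean and no separate BI standard deviation are given.
- **Margin:** "The study is designed to demonstrate a non-inferiority margin of 0.5".
- **Power:** "Group sample sizes of 18 in each group will achieve 95% power to detect non-inferiority using a two-sided, two-sample t-test with alpha 5" per cent. Enrolment is then set at 44 to allow for 20% drop-out.
- **True difference:** no number, only "The power calculation is based on the assumption that BI regimen will be non-inferior to MSI regimen for glycemic control".
- **Decision rule:** a "95% two-sided confidence interval (calculated on the basis of t-test or analysis of covariance) for the difference between BI and MSI treatment" is to be compared with the margin, which puts 2.5% on the non-inferiority side.

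Other sections hint at a direction for the true difference, but none gives a size. Section 3 (Objectives) says "A secondary aim of this study is to test that BI is superior to MSI for lowering HbA1c". Section 4 (Background) reports that, in the investigators' experience, "this simplified regimen is associated with less errors, improved glycemic control", although the same sentence ends by saying only that control is not compromised. Section 14 (Risks to Subjects) points the other way: "There is also a risk of less tight glycemic control in the BI group as compared to the MSI group".

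**The concern.** An SD of 0.9 with 18 per group gives a standard error of 0.30 for the difference in means. The margin of 0.5 is then only 1.67 standard errors from zero, which is less than the critical value of the test. Power of 95% is not plausible there unless BI is assumed to be clearly better than MSI, and no such assumption is stated.

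This sentence is the only justification for the sample size behind the primary objective. A reader who accepts it will expect a failure to show non-inferiority in about 1 trial in 20. If such a trial then gives an interval that includes 0.5, that reader may take it as evidence that BI is worse, when the trial was simply too imprecise to tell.

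**Working it through.** **Inputs (section 11).** SD = 0.9, taken as common to both groups; margin = 0.5; n = 18 per group; two-sided 5% t-test, so 2.5% on the non-inferiority side. The true difference d (BI minus MSI, negative when BI is better) is not stated, so it is varied.

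**Formulas.**
- SE = SD × √(2/n) = 0.9 × √(2/18) = 0.300
- df = 2 × 18 − 2 = 34; critical value t(0.975, 34) = 2.032
- Noncentrality = (0.5 − d)/0.300
- Power = probability that a noncentral t with 34 df exceeds 2.032

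**Trying to reproduce 95%.** At d = 0 the noncentrality is 0.5/0.300 = 1.667 and power is 36.7%. Simulating the confidence-interval rule also gives 36.7%. The stated figure is not reproduced. Other values of d:

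| d (BI minus MSI) | Noncentrality | Power, two-sided 5% |
|---|---|---|
| +0.2 | 1.000 | 16.2% |
| +0.1 | 1.333 | 25.3% |
| 0 | 1.667 | 36.7% |
| −0.1 | 2.000 | 49.3% |
| −0.2 | 2.333 | 62.1% |
| −0.3 | 2.667 | 73.6% |
| −0.4 | 3.000 | 83.0% |
| −0.5 | 3.333 | 89.9% |
| −0.6 | 3.667 | 94.5% |

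Power reaches 95% at d of about −0.61, a BI advantage larger than the margin itself.

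**Other readings.**
- One-sided 5%: 49.5% at d = 0, and 94.7% at d = −0.5.
- All 44 patients evaluable (22 per group), d = 0, two-sided 5%: 43.7%.
- Number per group needed at d = 0, two-sided 5%: 52 for 80% power (80.1%); 86 for 95% (95.2%, whereas 85 gives 94.96%).

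**Width of the interval.** With an observed SD of 0.9, the unadjusted half-width is 2.032 × 0.300 = 0.61. This exceeds 0.5, so an observed difference of exactly zero has an upper limit of 0.61 and does not show non-inferiority.

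**ANCOVA.** Section 11 allows covariate adjustment, including baseline HbA1c. With baseline correlation r (not stated; values assumed here), the residual SD is 0.9 × √(1 − r²) with 33 df. At d = 0:

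| r | Residual SD | Power | Half-width |
|---|---|---|---|
| 0.5 | 0.78 | 46% | 0.53 |
| 0.7 | 0.64 | 62% | 0.44 |
| 0.8 | 0.54 | 77% | 0.37 |

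The half-width falls below 0.5 only when r exceeds about 0.57, and 95% power needs r of about 0.89. Some combinations of both unstated inputs do reach 95%: r = 0.7 with d = −0.3 gives 95.2%, and r = 0.5 with d = −0.5 gives 96.2%.

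**The case against.** The best defence is that this is a missing input, not a miscalculation. Without a true difference, power is undetermined, and a BI advantage of about 0.61 would give 95% at the stated alpha. The superiority aim suggests the sponsor may have expected some advantage. There is also a plausible origin for 18 per group: a one-sided 5% test with a 0.5-point BI advantage gives 94.7%, which rounds to 95%. On this view, writing a zero difference into the plan substitutes the statistician's assumption for the sponsor's. Finally, recruitment was due to end on 8/31/2022 and the primary analysis was expected in 06/2023, the month of this document, so the observed interval now matters more than planned power.

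Part of this stands. The documents do not show how 18 was obtained, zero is an assumption and must be labelled as one, and the late date is a reason to ask for wording only. The defence does not rescue the sentence. The one-sided route needs an effect that is stated nowhere and an alpha that conflicts with both the two-sided test and the two-sided 95% interval in the same section. The superiority aim carries no effect size, and section 14 allows for a difference in the other direction. ANCOVA helps, but the power sentence names a t-test and no correlation is given.

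**Conclusion.** The concern holds. With SD 0.9, margin 0.5, 18 per group and a two-sided 5% t-test, the stated 95% power is unsupported. At an assumed true difference of zero it is 36.7%, a shortfall of about 58 percentage points (95 − 36.7 = 58.3), far beyond rounding. The chance of failing to show non-inferiority is then about 63%, not 5%.

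These figures assume normal data, a common SD of 0.9, 18 evaluable patients per group and no covariate adjustment. The conclusion would change only if the sponsor documents a BI advantage of about 0.61, a baseline correlation of about 0.89, or a suitable combination of the two; the plan states none of these. The correction is necessary because the primary objective relies on the figure.

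**What to change.** Keep the existing sentence for the record and add a dated correction in section 11, for example:

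> With 18 evaluable patients per group, SD 0.9, margin 0.5, an assumed true difference of zero and a two-sided 95% confidence interval (one-sided 2.5%), power is about 37%.

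If a BI advantage or a baseline correlation was assumed when the sample size was set, state its size and the power it gives next to this figure.

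As a supporting clarification, state how the 95% interval for BI minus MSI will be read:
- Upper limit below 0.5: non-inferiority shown.
- Interval includes 0.5: non-inferiority not shown, which alone is not evidence that BI is worse by more than the margin.
- Lower limit above 0.5: BI is worse by more than the margin.
- Lower limit above 0: BI is worse than MSI, whether or not non-inferiority is also shown.

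The cost is wording only, with no extra enrolment. The stated power becomes less favourable.

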Subjects will be recruited from the outpatient clinics of the University of Miami and Jackson Health affiliated clinics. Treating providers must have provided permission to include their patients into the study. The treating physician will identify the potential subject by screening through the clinic records or during the clinic visit. The study will be first introduced to potentially eligible patients by their treating physicians. After the treating physician speaks to the patient and if the patient agrees to be part of the study, the treating physician will refer the patient to the study team via verbal contact, phone contact, secure email or HER message. A member of study team will then speak with the patient and explain the study. This will take place either during the patient's clinic visit or over the phone. If the patient remains interested, patient chart will be accessed to screen for inclusion / exclusion criteria. If the patient qualifies for the study, a copy of the informed consent will be given or mailed. The patients will be encouraged to discuss participation with their primary care providers. They will be asked to call back if they have any questions. The consent

form will be signed at the time of first study visit that would often coincide with the patient's clinic visit.

Study Timelines

Patients will be recruited over a period of one year, 09/01/2018 – 8/31/2022.

All patients will be followed for a period of 6 month. The estimated date to complete the primary analysis will be 06/2023.

8) Study Endpoints*

Primary endpoint: Hemoglobin A1c (HbA1c) at 6 months after enrollment.

Secondary endpoint: 1. Average blood glucose levels (BG) during the study, 2. Incidence of hypoglycemia defined as any reported BG <70 mg/dl, 3. Incidence of severe hypoglycemia defined as any BG <54 mg/dl or patient requiring assistance to recover from hypoglycemia.

9) Procedures Involved*

Subject Enrollment

Subjects will be recruited from the outpatient clinics of the University of Miami and Jackson Health ACC clinics. Treating providers will inform the patients about the study. If a patient shows interest in participation, the study staff will review patient's chart for inclusion / exclusion criteria and provide the patient with more information about the study. Those, eligible for study and willing to participate, will have to provide a written informed consent.

Study Plan

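### The primary analysis cannot use the month-3 HbA1c of a patient who has no month-6 value, although 20% drop-out is expected and no missing-data method is stated

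*Combined protocol and SAP*

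**What the plan says.** - **Schedule.** Section 12 (Follow-up and Laboratory test): "HbA1C will be obtained at randomization and every 3 months after enrollment into the study". Over a 6-month study this means baseline, month 3 and month 6.
- **Endpoint.** Section 8: "Primary endpoint: Hemoglobin A1c (HbA1c) at 6 months after enrollment". Section 11 agrees: "The main outcome variable will be the HbA1c after 6 months of treatment".
- **Method.** Section 11: "The main analysis will be an independent sample t-test or an analysis of covariance". The possible covariates listed there include baseline HbA1c but not the month-3 value. Non-inferiority is read from a "95% two-sided confidence interval (calculated on the basis of t-test or analysis of covariance") against a margin of 0.5.
- **Drop-out.** Section 11: "Assuming a 20% drop-out rate, we plan to enroll 44 subjects into this study". Enrolling more patients is the only provision; no imputation, missing-data model or analysis population is described.
- **Withdrawal linked to HbA1c.** Section 14 takes BI patients whose HbA1c has not fallen below baseline in the first 3 months out of that group and puts them on MSI. No matching HbA1c rule is given for MSI patients. Study Timelines says all patients are followed for 6 months. The plan does not say whether month-6 values after such a move are collected or analysed.

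**The concern.** A t-test or ANCOVA of month-6 HbA1c drops any patient without that value unless it is imputed, and no imputation is planned. As written, the default is therefore a completer analysis. For a patient who leaves after month 3, the plan sets aside a recent HbA1c that is likely to predict the missing one well.

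Two things are at stake. The first is precision, in a trial with little to spare. The second is the direction of error. If BI patients who are doing badly at month 3 leave more often than comparable MSI patients, the remaining BI patients look better than the arm as randomised. The estimated deficit then shrinks towards a finding of non-inferiority.

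**Working it through.** **Inputs from the plan:** margin 0.5, SD 0.9, 1:1 allocation, 44 enrolled (22 per arm), 20% drop-out. **Assumed, because the documents give none:** the correlations between visits, the timing of drop-out and its dependence on HbA1c.

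**1. The plan's own figures.** 36 × 1.2 = 43.2, rounded up to 44. Dividing instead gives 36/0.8 = 45, so 44 is close enough. Expected completers are 44 × 0.8 = 35.2, or 17.6 per arm.

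The stated power ("Group sample sizes of 18 in each group will achieve 95% power to detect non-inferiority") does not reproduce at a true difference of 0. The standard error is 0.9 × √(2/18) = 0.30 and 0.5/0.30 = 1.67. With a two-sided 95% interval the power is Φ(1.67 − 1.96) ≈ 38%, or 36.7% by the exact t calculation. Reaching 95% with 18 per group would need an unstated BI advantage of about 0.6. This matters here only because it shows how scarce precision is.

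**2. Precision.** Let p be the correlation of month 3 with month 6 given baseline, n6 the number with a month-6 value and n3 the number with a month-3 value. In large samples the variance relative to baseline-adjusted ANCOVA is (1 − p²) + p² × n6/n3.

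Assume correlations of 0.6 (baseline–month 3), 0.5 (baseline–month 6) and 0.8 (month 3–month 6). Then p² = (0.8 − 0.6 × 0.5)² / [(1 − 0.36)(1 − 0.25)] = 0.25/0.48 = 0.521.

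| Drop-outs with a month-3 value | n6/n3 | Variance reduction |
|---|---|---|
| All | 0.80 | 0.200 × 0.521 = 10.4% |
| Half | 0.80/0.90 = 0.889 | 0.111 × 0.521 = 5.8% |
| None | 1 | 0% |

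With all drop-out after month 3, a month 3–month 6 correlation of 0.60 gives p² = 0.09/0.48 = 0.1875 and a reduction of 3.75%. A correlation of 0.85 gives p² = 0.3025/0.48 = 0.630 and 12.6%.

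Simulated trials of 22 per arm (correlations 0.6, 0.5 and 0.8, 20% random loss after month 3) gave standard errors of about 0.304 (t-test), 0.269 (ANCOVA) and 0.254 (three-visit model). The last step is worth about 4 completers (35.2/0.896 = 39.3). It narrows the 95% half-width by 1.96 × (0.269 − 0.254) ≈ 0.03.

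**3. Bias with unequal drop-out driven by month 3.** Large simulated samples, same correlations, BI truly 0.50 worse at months 3 and 6, 20% of MSI and 30% of BI lost. The log-odds of drop-out rise linearly with month-3 HbA1c.

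| Slope per SD | t-test | ANCOVA | Three-visit model, all loss after month 3 | Three-visit model, half lost before month 3 |
|---|---|---|---|---|
| 0.5 | 0.47 | 0.48 | 0.50 | 0.49 |
| 1 | 0.44 | 0.46 | 0.50 | 0.49 |
| 1.5 | 0.43 | 0.45 | 0.50 | 0.49 |
| 2 | 0.42 | 0.44 | 0.50 | 0.48 |

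With equal drop-out in both arms and a true difference of 0, all three methods are unbiased apart from simulation noise.

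**4. A mechanism closer to Section 14.** Suppose the 20% of BI patients with the worst month-3 change have no month-6 value and 20% of MSI values are missing at random. The month 3–month 6 correlation is 0.5 to 0.8, and the correlations with baseline are 0.3 to 0.5. At a true deficit of 0.5, the t-test gives 0.40 to 0.45 and ANCOVA 0.32 to 0.39. At a true difference of 0, they give −0.06 to −0.10 and −0.12 to −0.18. The model with baseline and month 3 returns the truth within 0.003. That accuracy relies on simulated normal data and on loss that depends only on observed values.

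**The case against.** The case against has real substance.

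- **Timing.** A reader might infer that every patient will have a month-3 value. The documents give only a schedule, and the Section 13 withdrawal criteria can be met before month 3. For patients lost that early nothing is recovered, so the gain can be zero. This stands.
- **Assumptions about drop-outs.** A reader might infer that the plan treats drop-outs as though they were completers. It says no such thing; the point rests on its silence. The description fits the t-test, whereas ANCOVA assumes similarity only given its covariates. This stands.
- **Bias is not automatic.** A reader might infer that any month-6 analysis is biased once drop-out relates to glycaemia. Step 3 shows otherwise: it takes drop-out that affects the arms differently. No section says that ordinary drop-out depends on month-3 HbA1c. Section 14 does supply a BI-only link, so the risk is plausible but not established.
- **Size.** The larger precision gain, from 0.304 to 0.269, comes from baseline adjustment, which the plan already permits. This stands.
- **Regimen switches.** Patients moved from BI to MSI may still have month-6 values. These would not be missing but would reflect the other regimen. The model does not settle their use, so the fix must.
- **Dates.** The document is dated 06/14/2023, recruitment was to end on 8/31/2022 and the primary analysis was due in 06/2023. This limits when the change can be made, but does not remove the gap.

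**Conclusion.** The point holds in a limited form. Month-3 HbA1c is scheduled, the primary methods cannot use it for a patient without a month-6 value, and nothing is said about missing data.

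The precision loss relative to ANCOVA is about 10 to 11% of variance at best under the central correlations. It falls to about 6% if half the drop-outs leave before month 3 and to 0% if all do. With all loss after month 3, it runs from about 3–4% to 13% over month 3–month 6 correlations of 0.60 to 0.85.

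The stronger reason to act is possible one-sided bias at the margin: about 0.43 to 0.46 against a true 0.50 at moderate dependence, in the direction of non-inferiority. This rests on assumed correlations and on drop-out that differs by arm. The documents do not support a claim that the planned analysis is biased whatever the drop-out pattern, or that using month 3 would make up the shortfall in power.

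**What to change.** In Section 11, before any comparison by arm:

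- Specify one primary analysis: a likelihood-based repeated-measures model of baseline, month-3 and month-6 HbA1c with arm-by-visit terms, a common baseline mean, unstructured covariance and small-sample degrees of freedom. Read the month-6 BI-minus-MSI 95% interval against 0.5.
- Keep the baseline-adjusted month-6 ANCOVA as a supportive analysis.
- State that month-6 values collected after a regimen switch stay in the randomised arm, with a sensitivity analysis that sets them to missing. The two answer different questions: the first compares the arms as randomised, switches included; the second extrapolates to continued BI.

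If results by arm have already been seen, report the model as a sensitivity analysis and say so.

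The change needs no new visit, sample or patient. Its costs are a slightly more complex model in 44 patients, no gain for those lost before month 3, and reliance on data being missing at random given the observed values. It does not repair the power shortfall.

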This will be a randomized controlled trial of elderly patients with T2DM currently inadequately controlled on an insulin regimen. After an informed consent, patients will be randomized in 1:1 ratio to either a control group (MSI) or a study group (BI). MSI group will receive four insulin injections per day that will include a long acting and a short acting insulin. BI group will receive only one injection of insulin glargine in the morning. The goal of treatment in both groups will be achieving an HbA1c <8% without any incidence of hypoglycemia. The study period after randomization will be 6 months.

Both groups will receive instructions about diet and exercise and all other treatments as per the current ADA standards. Patients will be advised to send their blood glucose data to the study team every 3-7 days. In addition, patients will be asked to complete the questionnaires for quality of life measures and patient satisfaction at baseline and after 6 months of treatment.

Insulin doses

The BI group will receive insulin glargine at a dose of 0.40 units/kg body weight once a day in the morning. If the total daily dose is more than 80 units, we will split the dose into two equal doses given morning and evening. The patient will be advised to monitor blood glucose (BG) four times daily: before meals and bedtime. The dose of insulin will be increased by 2 units every 3rd day to bring down the bedtime BG to <200 and fasting BG <130 mg/dL. Any BG <70 mg/dL or complaints of hypoglycemic symptoms at any time will lead to a decrease in insulin dose by 2 units or more.

The MSI group will receive insulin at a dose of 0.40 unit/kg body weight given 50% as insulin glargine at bedtime and 50% as rapid acting insulin divided into three doses before each major meal. The patient will be advised to monitor blood glucose (BG) four times daily: before meals and bedtime. The dose of insulin glargine will be adjusted every 3rd day to keep the fasting BG in 70-130 mg/dl range. The meal-time

rapid acting insulin doses will be adjusted to keep the pre-lunch and pre-dinner BGs <180 and bedtime BG <200 mg/dl.

10) Data and Specimen Banking*

The data or specimens will not be banked.

11) Data Management*

Statistical Analysis

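### Section 13 gives the glucose limb of the hypoglycemia withdrawal rule as 54 ng/dl where Section 8 has 54 mg/dl: very probably a one-letter slip, to be corrected

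*Combined protocol and SAP*

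**What the plan says.** Section 13 (Withdrawal of Subjects) sets a hypoglycemia criterion with two limbs, either of which suffices: "Patient with severe hypoglycemia needing assistance or BG below 54 ng/dl after two insulin dose adjustments". It is not restricted to one arm.

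Section 8 (Study Endpoints) defines the matching secondary endpoint: "Incidence of severe hypoglycemia defined as any BG <54 mg/dl or patient requiring assistance to recover from hypoglycemia". The milder event there is also in mg/dl: "Incidence of hypoglycemia defined as any reported BG <70 mg/dl".

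Section 14 (Risks to Subjects) repeats the withdrawal rule for one arm only: "Any severe hypoglycemia in the BI group after two dose adjustments will lead to withdrawal from the study", after which the patient moves to the MSI regimen.

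Section 9 (Procedures Involved) has further low-glucose guidance. The BI dosing paragraph says: "Any BG <70 mg/dL or complaints of hypoglycemic symptoms at any time will lead to a decrease in insulin dose by 2 units or more". A titration target with a floor appears in the MSI paragraph: "The dose of insulin glargine will be adjusted every 3rd day to keep the fasting BG in 70-130 mg/dl range". For both arms, "The goal of treatment in both groups will be achieving an HbA1c <8% without any incidence of hypoglycemia".

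**The concern.** The same threshold appears in two units. Sections 8 and 13 use the same number, 54, with the same alternative of needing assistance, and plainly describe the same clinical event. Only the unit differs, and the Section 13 unit is not a plausible one for blood glucose.

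The sentence matters more than background text would, because it decides when a patient over 65 on titrated insulin leaves the study. Since Section 14 restates the rule for the BI arm alone, Section 13 is the only explicit hypoglycemia withdrawal rule for the MSI arm. It is also a reference against which withdrawals will be reported.

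**Working it through.** **1. Size of the discrepancy.** 1 mg = 1,000,000 ng, so

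54 ng/dl = 54 / 1,000,000 = 0.000054 mg/dl.

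Ratio to the Section 8 threshold: 54 / 0.000054 = 1,000,000. No real glucose reading falls below 0.000054 mg/dl, so the glucose limb, taken literally, cannot be met.

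**2. Which unit is the odd one out.** Glucose values or ranges with a unit attached:

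| Place | Values | Unit |
|---|---|---|
| Section 8 | <70; <54 | mg/dl |
| Section 9, BI dosing | fasting <130; <70 | mg/dL |
| Section 9, MSI dosing | 70-130; bedtime <200 | mg/dl |
| Section 13 | 54 | ng/dl |

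The total is 2 + 2 + 2 + 1 = 7, of which six are in mg/dl and one is in ng/dl. The intended unit is not in doubt.

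**3. What a literal reading would leave uncovered.** Each case is taken after two dose adjustments.

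| Patient | Rule that still applies | Withdrawn on a literal reading? |
|---|---|---|
| Either arm, needs assistance | Section 13, assistance limb | Yes |
| BI, glucose <54 mg/dl, no assistance | Section 14, using the Section 8 definition | Yes |
| MSI, glucose <54 mg/dl, no assistance | None stated | No |

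Only the last row is a gap. Even there the plan is not silent on low glucose: glargine is titrated to a fasting range that starts at 70 mg/dl, and avoiding hypoglycemia is a treatment goal in both arms.

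**4. Whether patients were still under the rule.** Section 7 plans recruitment to 8/31/2022 and six months of follow-up, which ends about 2/28/2023. This version is dated 06/14/2023, which is 31 + 30 + 31 + 14 = 106 days later. The documents do not confirm that the planned dates were kept.

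**5. Link to the statistics.** The sample-size and power statement in Section 11 does not use the threshold, so there is no planned figure to reproduce or revise.

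**The case against.** The strongest reply is that nobody would be misled. Patients check their glucose four times a day against mg/dl targets, Section 8 supplies the right unit for the same event, and Section 14 backs up the BI arm. On the planned dates, follow-up had ended before this version was dated. All of that stands. It makes the point small, but it does not make the unit right.

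It could also be said that the wrong letter arose when the PDF was read. That cannot be wholly excluded for a single character. However, the surrounding text is clean and the other six units were read correctly, so a slip in the source is more likely. A look at the source file would settle it.

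Three stronger readings are tempting, and the documents do not support them:

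- **That the withdrawal criterion as a whole can never be met, or that the million-fold factor measures harm.** Only the glucose limb fails on a literal reading. The factor is a property of the unit prefix.
- **That Section 13 shows a pattern of unit errors**, because its hyperglycemia criterion, "Patient with uncontrolled hyperglycemia >400 despite two insulin dose adjustments", carries no unit. A missing unit conflicts with nothing, and mg/dl is the unit used for glucose everywhere else. It is not an error.
- **That the MSI arm has no protection against low glucose.** It lacks a second explicit withdrawal rule, but it has the assistance limb, the titration floor and the common treatment goal.

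**Conclusion.** The point holds as a correction to one unit. Section 13 is wrong as written and conflicts with Section 8; the intended threshold is 54 mg/dl. Read literally, the loss is confined to MSI patients with glucose below 54 mg/dl who need no assistance after two dose adjustments.

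The practical effect is probably negligible, on the assumption that staff applied the rule in mg/dl, as any clinician would. A reader might infer that the slip altered who was withdrawn, or that it biases the HbA1c comparison. Nothing in the documents shows that the literal value was ever applied, and there is no effect on the primary analysis. If the planned dates held, the correction serves the record and the reporting of withdrawals, not patients still in follow-up.

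Confidence that the unit is wrong is high for the text as it stands, subject to the small chance of a misread character.

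**What to change.** In Section 13, change ng/dl to mg/dl, so that the glucose limb is 54 mg/dl and agrees with Section 8 in both arms. This is a one-letter edit that needs no clinical judgment and has no operational cost. Nothing else in Section 13 has to change for this point.
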